5 STUDY OBJECTIVES

5.1 PRIMARY OBJECTIVE

The primary objective of this study is to assess the efficacy of bupropion in reducing methamphetamine use in subjects with methamphetamine dependence (DSM-IV criteria). The null hypothesis is that bupropion treatment, compared to placebo, will result in a statistically significant difference (two-sided p < 0.05) in the weekly proportion of methamphetamine-free urines.

5.2 SECONDARY OBJECTIVES

Secondary objectives include:

- 1. Determining the safety of bupropion in the study population.
- 2. Assessing the efficacy of bupropion in other measures of success in the reduction of methamphetamine use including the proportion of successful subjects with 3 consecutive weeks of negative urine samples as measured by 9 consecutive negative urine samples for methamphetamine, the weekly mean proportion of non-use days assessed by self report of use, the largest number of consecutive methamphetamine non-use days, and reductions in use as compared to baseline.

- 3. Assessing the efficacy of bupropion in the reduction in the severity of methamphetamine dependence (assessed by ASI-Lite and self and observer scored CGI) and craving (assessed by BSCS), and severity of depression (assessed by HAM-D) as compared to placebo control.
- 4. Assessing the efficacy of the bupropion in reducing the proportion of use-days of other substances of abuse (opiates, marijuana, cigarette smoking, alcohol, and cocaine) as determined by SUR and the number of negative urines for other substances of abuse (amphetamines, cocaine, opiates, tetrahydrocannabinol, benzodiazepines, and barbiturates) by urine drug screen, or negative alcohol breathalyzer tests.
- 5. Assessing the effects on HIV risk taking behaviors.
- 6. Assessing the effects of bupropion on neurocognitive functions.
- 7. Assessing the reduction in methamphetamine use as a function of the resolution of depression in bupropion *versus* placebo groups.

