3 PROTOCOL SYNOPSIS

STUDY OBJECTIVES: To assess the efficacy and safety of bupropion in reducing methamphetamine use in subjects with methamphetamine dependence. It is hypothesized that bupropion treatment, compared to placebo, will be associated with fewer days of methamphetamine use as measured by quantitative urine analysis for methamphetamine.

STUDY DESIGN: This is a double-blind, placebo-controlled, parallel-group design study in which, after screening and a 2-week baseline period, 150 subjects will be randomly assigned to either placebo or bupropion for 12 weeks with a follow-up assessment 4 weeks after treatment completion. Five clinical research sites will each recruit approximately 30 participants into the trial. Adaptive randomization will be used to balance treatment groups based on gender, historical self-report of methamphetamine use (prior use in the last 30 days \leq 18 *versus* > 18), and severity of depression (HAM-D score \leq 12 *versus* >12).

STUDY POPULATION: 150 individuals (30 per site) with Diagnostic and Statistical Manual of Mental Disorders Fourth Edition (DSM-IV) criteria for methamphetamine dependence determined by structured clinical interview (SCID) will be randomized into one of two treatment groups. Males and females, between 18 and 65 years-of-age, with 1 methamphetamine positive urine specimen provided during the 2-week baseline period prior to randomization who verbalize the ability to understand and provide written informed consent will be included.

TREATMENTS: Subjects randomized to bupropion treatment will receive 150 mg of sustainedrelease bupropion once daily for 3 days then twice daily for a total of 300 mg for a total of 12 weeks (dose taper will be performed the last 3 days of the 12 weeks to 150 mg per day). Subjects randomized to the placebo arm will receive matched placebo tablets according to the same schedule. All subjects will receive manual-guided cognitive behavioral therapy (CBT) thrice weekly during the 12 weeks of treatment.

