8.2 OUTCOME/RESPONSE MEASURES

The principal outcome measure is urine methamphetamine analysis. This outcome measure was selected as the primary study endpoint to examine the effect of treatment on an objective measure of reduction in methamphetamine use. However, as methamphetamine has an excretion half-life of 12 to 14 hours, carryover could result in a positive urine specimen even when the subject has not used. Therefore, this is potentially a conservative outcome measure of treatment effect.

Data from previous methamphetamine pharmacokinetic studies, as well as other outpatient studies, will be used to develop rules/algorithm for determining new versus old (carryover) use utilizing urine methamphetamine levels. As the urine samples in this study are being analyzed quantitatively for methamphetamine, if an algorithm is developed to determine new use versus carryover, this algorithm will be used for additional analyses.

Secondary outcome measures include:

- 1. Measuring reductions in drug use assessed by self-report of use;
- 2. Assessing the severity of methamphetamine dependence using the ASI-Lite and self and observer scored CGI;
- 3. Assessing changes in craving (determined BSCS);
- 4. Assessing the severity of withdrawal symptoms (determined by MAWQ),
- 5. Assessing changes in depression (determined by HAM-D score) and the association of these changes with reductions methamphetamine use;
- 6. Assessing the effect on the use days of other substances of abuse (opiates, marijuana, cigarette smoking, cocaine, and alcohol) as determined by self-report and negative urine (opiates, tetrahydrocannabinol, amphetamines, cocaine, benzodiazepines, or barbiturates) or alcohol breathalyzer results;
- 7. Assessing the effect on HIV risk taking behaviors;
- 8. Assessing the effect on cognitive functions; and
- 9. Safety of bupropion in the study population.

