9.1 INCLUSION CRITERIA

Participants must:

- 1. Be males and/or females, between 18 and 65 years-of-age.
- 2. Have a DSM-IV diagnosis of methamphetamine dependence as determined by SCID.
- 3. Have at least 1 amphetamine or methamphetamine positive urine specimen (> 1000 ng/mL) within the two-week baseline period prior to randomization with a minimum of 4 samples tested.
- 4. Be willing and able to comply with study procedures.
- 5. Be able to verbalize understanding of consent form, able to provide written informed consent, and verbalize willingness to complete study procedures.
- 6. Be seeking treatment for methamphetamine dependence.
- 7. If female, have a negative pregnancy test and agree to use one of the following methods of birth control:
 - a. oral contraceptives
 - b. patch
 - c. barrier (diaphragm or condom) with spermicide or condom only
 - d. intrauterine progesterone or non-hormonal contraceptive system
 - e. levonorgestrel implant
 - f. medroxyprogesterone acetate contraceptive injection
 - g. surgical sterilization
 - h. complete abstinence from sexual intercourse

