Following randomization, during the treatment phase of the study and at each of the follow-up visits, urine will be collected 3 times per week (generally Monday, Wednesday, and Friday, barring holidays and schedule conflicts) and NWT will screen the first sample collected each week for cocaine, methamphetamine/amphetamines, tetrahydrocannabinol, barbiturates, opiates, and benzodiazepines. NWT will screen all samples for amphetamines/methamphetamine and quantitative creatinine, and NWT will quantitate amphetamines and methamphetamine for all samples, which screen positive by NWT for methamphetamine/amphetamines.

All specimens collected during this time frame and screened positive by NWT for methamphetamine/amphetamines will be subjected to methamphetamine quantitative analysis performed at NWT for the determination of "new use." The back-up sample retained at the site will be stored frozen until the NIDA data-coordinating center has notified the site that it can be disposed.

Urine Toxicology Screen Using an Onsite Testing Device. During the screening and baseline period, urine will be collected 3 times per week (generally Monday, Wednesday, and Friday, barring holidays and schedule conflicts). After the backup aliquot and central laboratory testing aliquot has been taken, these samples will be analyzed using an on-site testing device (tetrahydrocannabinol, methamphetamine, cocaine, amphetamines, barbiturates, opiates, benzodiazepines, tricyclics, and phencyclidine). Samples positive for amphetamine (the onsite testing device has a cutoff of greater than or equal to 1000 ng/mL) will be considered as positive for methamphetamine for inclusion criteria purposes.

During treatment and after the backup aliquot and central laboratory testing aliquot has been taken, the first urine sample collected each week will be analyzed using an on-site testing device.

A frozen aliquot of every sample will be stored at the site. At treatment termination and followup, samples will be sent to a central lab for analysis, be subjected to onsite testing, and an aliquot will be frozen on site as back up. Results of on-site testing will be provided to the clinical staff as well as the investigative staff for the safety of the subjects.

Medical Urinalysis. Urine will be collected and analyzed for specific gravity, pH, blood, protein, glucose, ketones, leukocytes, and nitrites. The analysis will be conducted at a central clinical laboratory.

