15.3 STATISTICAL HYPOTHESES

The null hypothesis is that bupropion treatment, compared to placebo, will result in a statistically significant difference (two-sided p < 0.05) in the weekly proportion of methamphetamine-free urines. Hypotheses for the secondary outcome measures include that bupropion treatment, compared to placebo, will reduce the pattern and quantity of methamphetamine use by various measures of success, reduce the severity of methamphetamine dependence (assessed by ASI-Lite and self and observer scored CGI), methamphetamine craving (assessed by BSCS), severity of

withdrawal symptoms (assessed by MAWQ), and depression (assessed by HAM-D), and decrease the amount of use-days of other substances of abuse (opiates, marijuana, nicotine, alcohol, and cocaine) as determined by self report of use or urine drug determination (amphetamines, cocaine, opiates, tetrahydrocannabinol, benzodiazepines, and barbiturates).

There is no generally accepted definition of clinically significant improvement in the treatment of methamphetamine dependency. The primary and secondary objectives are intended to explore various aspects of response to therapy and to help define a clinically meaningful response. The secondary objectives also add a measure of clinical relevance to the reduction of use by exploring the effect of therapy on psychosocial aspects of methamphetamine dependency.

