15.4.2 Secondary Outcomes Measures

Effect on methamphetamine and other drug use during the 12-week treatment period

- **A.** Log weekly median quantitative methamphetamine level.
- **B.** The proportion of successful subjects with different patterns in the reduction in drug use examined as follows:
 - 1. Proportion of subjects with 3 consecutive weeks of abstinence as measured by 9 consecutive methamphetamine negative urine samples.
 - 2. Proportion of subjects who reduce the overall proportion of methamphetamine quantitative urine concentration to 50% or less of his/her baseline rate.
 - 3. Proportion of subjects who reduce the overall proportion of methamphetamine quantitative urine concentration to 25% or less of his/her baseline rate.
- **C.** Weekly mean proportion of methamphetamine non-use days based on subjects self report of use (SUR) during the 12-week treatment period.

- **D.** The maximum number of consecutive methamphetamine non-use days by subjects self report of use (SUR).
- **E.** The proportion of methamphetamine negative urines during the 12-week period.
- **F.** Weekly mean proportion of non-use days of other drug use, by other drug according to SUR.
- G. Proportion of negative urines or alcohol breathalyzer results for other drug use, by drug.

Reduction in the severity of methamphetamine dependence, craving, and withdrawal

- H. CGI-O scores.
- I. CGI-S scores.
- J. ASI-Lite scores.
- K. BSCS scores.
- L. MAWQ scores

Severity of Depression

M. HAM-D scores.

Changes in Cognitive Functions

N. Change in cognitive function at study end compared to baseline.

HIV Risk Taking Behaviors

O. Change in HRBS scores since baseline.

Treatment Retention

P. Number of days in treatment.

Safety of Bupropion

Q. AEs, laboratory data, physical exams, and vital signs.

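### Amphetamines are listed as another substance of abuse, but the central urine screen reads them together with methamphetamine, so a methamphetamine effect would be reported a second time as an effect on another drug

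*Protocol*

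**What the plan says.** **The outcome.** Section 5.2, item 4, names among its measures the "number of negative urines for other substances of abuse (amphetamines, cocaine, opiates", then tetrahydrocannabinol, benzodiazepines and barbiturates, by urine drug screen. Section 15.2 repeats this. Section 15.3 speaks of "urine drug determination (amphetamines, cocaine, opiates" and the same remaining classes. Section 8.2, item 6, has "negative urine (opiates, tetrahydrocannabinol, amphetamines, cocaine, benzodiazepines, or barbiturates" among the results for other substances. The Synopsis gives the same six classes but calls the method quantitative urinalysis at a central laboratory.

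Measure G in Section 15.4.2 is "Proportion of negative urines or alcohol breathalyzer results for other drug use, by drug". It names no drug, so its list comes from the objective. Section 15.6.1 assigns it a chi-square test.

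**The assay.** Section 13.6.14 says that during treatment "NWT will screen all samples for amphetamines/methamphetamine and quantitative creatinine". The first sample of each week is also screened for the other five classes, and there too methamphetamine and amphetamines appear as a single slashed entry. Samples positive on that combined entry go on to quantitation of both analytes. The on-site device, used on the first sample of each week, lists the two separately.

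**The concern.** An other-drug outcome is meant to show whether treatment changes use of something besides the target drug. If the reading for that drug cannot differ from the reading for the target drug, the comparison adds no information, yet it will be tabulated as a separate result. A favourable methamphetamine finding would then seem to be corroborated by reduced use of a second drug that was never measured separately. Because the listing occurs in five places, it is not a single slip, and an analysis that followed the protocol would carry it through.

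**Working it through.** The protocol states no figure for this outcome, so there is none to reproduce. The check sets its rules side by side and counts the shared samples.

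1. **Is an amphetamine comparison planned?** Yes. Amphetamines are one of six urine-screened classes in objective 4, measure G is analysed by drug, and Section 15.6.1 gives the test.

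2. **Which reading would supply it?** Objective 4 names the urine drug screen. Sections 13.3 and 13.6.14 place the central drug screen on the first sample of each week.

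3. **How many samples are shared?** Scheduled treatment samples: 12 weeks × 3 = 36. First-of-week samples: 12 weeks × 1 = 12. Share: 12/36 = one third. If measure G instead used every sample screened for amphetamines/methamphetamine, the shared set would be all 36.

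4. **What follows on those samples?** Let S be the combined central screen result. By the screen route, amphetamine negative means S negative, and methamphetamine screen negative also means S negative. Writing p_P and p_B for the proportions of samples with S negative on placebo and bupropion, the between-arm difference is p_B − p_P under either label, whatever the rates. As an illustration with assumed rates, if S were positive in 60% of samples on placebo and 45% on bupropion purely through methamphetamine use, both rows would show 60 − 45 = 15 points. Any other pair of rates behaves the same way, so this shows the mechanism and is not a forecast.

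5. **Is this the primary outcome again?** Not exactly. Section 15.4.1 scores all three weekly samples on an ordinal scale with a 300 ng/mL cutoff, and Section 15.6.1 analyses that score by GEE. Measure G on the drug screen uses one sample a week and a chi-square test. The two are strongly related, but they are different variables.

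6. **Does anything else separate the two drugs?** The Substance Use Report (Section 13.6.23) has no amphetamine item. That alone says little, since benzodiazepines and barbiturates are also absent from it, but those two have their own urine readings. Central quantitation could separate the analytes, but it follows only a positive combined screen, and the protocol does not tie it to an amphetamine-negative urine.

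7. **Do the two stated methods agree?** No. The Synopsis says quantitative urinalysis for all six classes and objective 4 says screen. Among those classes, Section 13.6.14 describes quantitation only for amphetamines and methamphetamine.

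**The case against.** The strongest reply is that the means of separating the drugs already exist. Both analytes are quantified after a positive combined screen, the on-site device lists them separately, and the Synopsis names quantitative urinalysis as the method. What is missing would then be a scoring rule, which may stand in an analysis plan that is not at hand. This reply stands in part: a reader might infer that the objective cannot be answered for amphetamines, and the documents do not support that. But the point does not rest on a missing rule. The protocol itself fixes amphetamines as another drug and names, in objective 4, a route on which the central reading is shared.

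A reader might also infer that a null methamphetamine result would force a null amphetamine result. It would not. The primary outcome differs in samples, cutoff, scale and test, so the two results will tend to agree without having to.

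A third tempting inference is that the entry criterion is defective because it accepts amphetamine. Section 9.1 reads "Have at least 1 amphetamine or methamphetamine positive urine specimen (> 1000 ng/mL) within the two-week baseline period", while the Synopsis asks for candidates "with 1 methamphetamine positive urine specimen provided during the 2-week baseline period prior to randomization". Section 13.6.14 bridges the two: an on-site amphetamine positive "will be considered as positive for methamphetamine for inclusion criteria purposes". Section 9.1 separately requires a SCID diagnosis of methamphetamine dependence. This is a stated choice. The bridging rule is also limited to inclusion and runs from amphetamine to methamphetamine, so it cannot carry the outcome argument, which rests on the combined central screen.

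Finally, this is one drug within one of measures A to Q, and Section 15.3 describes the objectives as exploratory. That limits the weight of the point without removing it.

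**Conclusion.** The point holds for the route that objective 4 names. On the central weekly drug screen, the amphetamine result and the methamphetamine screen result are one reading, so a methamphetamine effect would be reported again as an effect on another drug. It affects one of six urine-screened classes in one secondary objective, on 12 of 36 scheduled treatment samples. The primary analysis is unaffected, and the overlap with it is strong but not exact.

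The conclusion assumes that the slashed entry in Section 13.6.14 denotes a single screen result, as its wording on samples that screen positive suggests, and that measure G is scored from the central screen. If it were scored from the on-site device or the quantitation, the identity would no longer be automatic, but the protocol would need to say so. The change is worth making because it is specific and nearly free.

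**What to change.** Do one of the following:

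- Remove amphetamines from the other-substance urine lists in the Synopsis, Section 5.2 item 4, Section 8.2 item 6, Section 15.2 item 4 and Section 15.3. Measure G then follows by reference and needs no edit.
- Keep an amphetamine outcome but define it from the separate central quantitation, for example as amphetamine found without methamphetamine. State its limit: a subject who uses both drugs would be scored negative for the other drug.

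In either case, reconcile the Synopsis (quantitative urinalysis) with Section 5.2 (urine drug screen), so that one method is named for each drug.

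The first option costs one secondary comparison. The second costs a definition. Neither needs a new assay or visit.

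No change to inclusion criterion 3 is proposed. Section 15.7 shows that at least 50 subjects had already been randomized, so altering it would be an eligibility change during the trial and not an edit of wording. At most, the entry wording in the Synopsis and Sections 12.2 and 13.2 should be reconciled with Sections 9.1 and 13.6.14.

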6 IND HOLDER

This study will be conducted under an IND held by the Principal Investigator, [name].

7 STUDY SITES

The trial will be conducted as a multi-center 5-site study coordinated by the University of California, Los Angeles- Integrated Substance Abuse Programs and conducted by investigators associated with 5 organizations including the University of Missouri-Kansas City, Kansas City, Missouri, University of Hawaii (Queens Hospital) Honolulu, Hawaii, Friends Research Institute (Matrix Institute on Addictions) Costa Mesa, California, South Bay Treatment Center, San Diego, California, and the Iowa Health Systems (Office of Research, Lutheran Hospital) Des Moines, Iowa.

8 STUDY DESIGN

8.1 EXPERIMENTAL DESIGN

This is a double-blind, placebo-controlled, two arm study with a parallel-group design in which, after screening and a 2-week baseline period (the screening period may be extended to 4 weeks if entry criteria are not met in the first two weeks), subjects will be randomly assigned to treatment with either placebo or bupropion for 12 weeks with a final follow-up assessment 4 weeks after completion of treatment. Adaptive randomization will be used to balance treatment groups based on gender, historical self-report of methamphetamine use (prior use in the last 30 days \leq 18 *versus* > 18), and severity of depression (HAM-D score \leq 12 *versus* >12). All subjects will receive a base of standardized, manual-driven CBT (a 90-minute group session) three-time-a-week used in our other stimulant trials (Huber *et al.*, 1997; Rawson *et al.*, 1995; Shoptaw *et al.*, 1994) during the 12-week treatment period.

8.2 OUTCOME/RESPONSE MEASURES

The principal outcome measure is urine methamphetamine analysis. This outcome measure was selected as the primary study endpoint to examine the effect of treatment on an objective measure of reduction in methamphetamine use. However, as methamphetamine has an excretion half-life of 12 to 14 hours, carryover could result in a positive urine specimen even when the subject has not used. Therefore, this is potentially a conservative outcome measure of treatment effect.

Data from previous methamphetamine pharmacokinetic studies, as well as other outpatient studies, will be used to develop rules/algorithm for determining new versus old (carryover) use utilizing urine methamphetamine levels. As the urine samples in this study are being analyzed quantitatively for methamphetamine, if an algorithm is developed to determine new use versus carryover, this algorithm will be used for additional analyses.

Secondary outcome measures include:

- 1. Measuring reductions in drug use assessed by self-report of use;
- 2. Assessing the severity of methamphetamine dependence using the ASI-Lite and self and observer scored CGI;
- 3. Assessing changes in craving (determined BSCS);
- 4. Assessing the severity of withdrawal symptoms (determined by MAWQ),
- 5. Assessing changes in depression (determined by HAM-D score) and the association of these changes with reductions methamphetamine use;
- 6. Assessing the effect on the use days of other substances of abuse (opiates, marijuana, cigarette smoking, cocaine, and alcohol) as determined by self-report and negative urine (opiates, tetrahydrocannabinol, amphetamines, cocaine, benzodiazepines, or barbiturates) or alcohol breathalyzer results;
- 7. Assessing the effect on HIV risk taking behaviors;
- 8. Assessing the effect on cognitive functions; and
- 9. Safety of bupropion in the study population.

Self-report of use has been utilized and considered as a valid outcome measure for other substance abuse studies for which biological measurements of abstinence cannot logistically be utilized in outpatient studies (alcohol abuse for example). Self-report of use has a good correlation to the use profile provided by measurements of urine benzoylecgonine (a cocaine metabolite) in cocaine medication trials. Therefore, self-report of methamphetamine use is considered a reliable alternative measure of the treatment effect that may have greater sensitivity than urine methamphetamine test results to discern small but significant treatment effects. In addition, the HRBS will be assessed for population descriptive and other scientific uses and not as a primary or secondary outcome measure.

